9.6.1 Requirements for Immediate Reporting of Serious Adverse Events

The minimum reporting requirements for immediate reporting of SAEs include:

- Identifiable subject.
- Suspected medicinal product and / or procedure.
- Event term.
- Identifiable reporting source.

In addition, the investigator must:

- Report all SAEs to the relevant institutional review board (IRB) / independent ethics committee (IEC) within the timeframe specified by the IRB / IEC.
- Submit follow-up reports to CSL Clinical Safety and Pharmacovigilance until the SAE has resolved, or, in the case of permanent impairment, until stabilized.
- Ensure that the causality assessment for all SAEs is entered in the eCRF.

If the minimum requirements for reporting are fulfilled, the investigator should not wait to receive additional information to fully document the event before notifying CSL.

When submitting SAE reports and any other related reports (eg, discharge summaries) to CSL, subjects should be identified only by their subject number and study number. The investigator should not include the subject's name, date of birth, or address.

In cases of death, the investigator should supply CSL and the IEC / IRB (as applicable) with any additional information as it becomes available (eg, autopsy reports and detailed medical reports).

The procedure to be followed if an ongoing AE becomes an SAE after the end of the observation period for AEs is described in [Section 9.9](#).

9.7 Other Significant Event Reporting

9.7.1 Overdose

Details (ie, volume, location of injections, injection rate) of an overdose of rVIII-SingleChain or any concomitant therapy must be recorded in the eCRF. Any overdose that is considered by the investigator to be medically significant must be reported as an SAE (see [Section 9.6](#)).

Any AE related to rVIII-SingleChain associated with ≥ 2 times the prescribed dose is considered an overdose.

9.7.2 Pregnancy and Lactation

A female partner of a male subject who becomes pregnant while participating in the study, or up to and including 28 days after the last dose of rVIII-SingleChain, must notify the investigator immediately.

CSL must be notified within 5 days of the investigator becoming aware of the pregnancy.

Whenever possible, a pregnancy in a female partner of a male subject exposed to rVIII-SingleChain should be followed to term so as to assess any potential occurrence of congenital anomalies or birth defects. Any follow-up information, including premature termination and the status of the mother and child after delivery, should be reported by the investigator to CSL using a Pregnancy Reporting / Outcome Form.

9.8 IRB / IEC Reporting Requirements

The time frame within which an IRB / IEC must be notified of deaths and investigational product-related unexpected SAEs is stipulated by each IRB / IEC. It is the investigator's responsibility to comply with the requirements for IRB / IEC notification. CSL will provide investigators with all details of all SAEs reported to regulatory authorities.

9.9 Follow-up of Adverse Events

Every effort should be made to follow-up subjects who continue to experience an AE or an SAE on completion of the study until either the AE resolves or stabilizes, or until 28 days after the final administration of rVIII-SingleChain, whichever is sooner. All follow-up information (and attempted follow-up contacts) should be documented in the subject's medical records. Details of the subject's progress should also be submitted to CSL Global Clinical Safety and Pharmacovigilance.

For the specific follow-up procedures for inhibitor SAEs in Arm 2 (PUPs) after the End of Study Visit, see Section 9.10.

9.10 Follow-up of Inhibitor SAEs in Arm 2 (PUPs)

PUPs in Arm 2 who develop an inhibitor SAE (ie, low-titer or high-titer inhibitors confirmed by the central laboratory) will be followed up for **28 days after their End of Study Visit**. All follow-up information (and attempted follow-up contacts) should be documented in the subject's medical records and submitted to CSL Global Clinical Safety and Pharmacovigilance. At a minimum, the following specific information should be documented and submitted:

- Information on last inhibitor titer.
- Details and outcome of major / life-threatening bleeding episodes.

- Hemophilia treatment since End of Study Visit:
 - Treatment modality (on-demand, prophylaxis).
 - Currently receiving CCI [REDACTED]
 - CCI [REDACTED]
 - Treatment with bypassing agents (yes, no).
- AEs since End of Study Visit.
- Development of inhibitor after previous eradication. In the event of inhibitor development after previous eradication, this will be considered a new SAE and should be reported as such.

10 Assessments

10.1 Subject Characteristics

Subject characteristics to be evaluated will include:

- Demographic data (eg, sex, race, height, body weight).
- Medical and surgical history.
- History of hemophilia A.

10.2 Efficacy Assessments

The efficacy of rVIII-SingleChain treatment in the prophylaxis and treatment of bleeding episodes will be assessed based on the following:

- Total consumption of rVIII-SingleChain (number of EDs and mean IU/kg per year per subject and per bleeding episode) and consumption per routine prophylaxis, on-demand treatment, and surgery.
- Number of traumatic and non-traumatic bleeding episodes.
- Investigator's clinical assessment of hemostatic efficacy for treatment of bleeding episodes (4-point scale).
- Number of rVIII-SingleChain injections required to achieve hemostasis.
- Investigator's clinical assessment of hemostatic efficacy for treatment during surgery (4-point scale).

10.3 Safety Assessments

Safety will be assessed based on the following variables:

- AEs and SAEs.
- Serum chemistry and hematology.
- Physical examination.
- Vital signs.
- Inhibitors to FVIII.
- Antibodies against rVIII-SingleChain.
- Antibodies against CHO proteins.
- Subject / caregiver assessment of local tolerability.
- **Arms 2 and 3 only:** investigator assessment of local tolerability for rVIII-SingleChain injections administered at the clinic.

Clinical laboratory tests will be performed at timepoints as detailed in the Schedules of Assessments. More frequent evaluations may be performed, if clinically indicated, at the discretion of the investigator.

10.4 Pharmacokinetic and Pharmacodynamics

- IR (see [Section 8.6](#)).

10.5 Other Assessments

- FVIII activity level at Screening (Arms 2 and 3), if not available in subject's medical records. FVIII activity level must be determined at the local laboratory, and the result must be available before enrollment.

11 Statistics

11.1 Sample Size Estimation

The sample size was based on the EMA guidelines for the clinical investigation of recombinant and human plasma-derived factor VIII products [EMA, 2011]. Therefore, no sample size calculations were performed. The target enrollment is at least 200 PTPs (Arms 1 and 3) completing at least 100 EDs during enrollment in all CSL-sponsored rVIII-SingleChain studies and 24 PUPs (Arm 2) completing 50 EDs of rVIII-SingleChain in this study. Thus, the study will enroll at total of least 224 subjects with severe hemophilia A.

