al., 2016], the number of suitable patients especially previously untreated patients (PUPs) to be enrolled in clinical trials is problematic. Hence, the conduct of sufficiently informative clinical trials in PUPs to estimate important characteristics of single products is considered difficult. Therefore the obligation to perform clinical trials in PUPs for marketing authorisation purposes has been deleted [EMA, 2108].” CSL Behring has reached an agreement with the EMA Paediatric Committee through a request for modification of the pediatric investigational plan (PIP) to stop enrolling subjects into Study CSL627_3001 and to continue treatment of the subjects currently enrolled. In addition, to ensure that patients achieve PTP status at the end of participation in Arm 2, all PUPs were to achieve 150 EDs to rVIII-SingleChain. However, based on a recently published report of risk periods for inhibitor development in 1038 PUPs with severe hemophilia A, there is now strong evidence from the largest prospective cohort study of PUPs to show that almost all inhibitors have developed by 75 EDs of treatment [Van den Berg et al., 2019]. CCI [REDACTED]

The study population will consist of a total of at least 224 subjects with severe hemophilia A (FVIII activity level of < 1%). Of these, at least 200 are PTPs who have participated in a previous CSL-sponsored study with rVIII-SingleChain (ie, Arm 1) or who are not currently enrolled in a rVIII-SingleChain study (Arm 3), and at least 24 are PUPs (ie, Arm 2).

In line with the EMA guideline, Arm 2 of the present study was opened for enrollment after the following information became available:

- a) Independent Data Monitoring Committee (IDMC) approval that the data from at least 20 PTPs < 12 years of age with 50 EDs each (including at least 10 PTPs 0 to < 6 years of age and at least 10 PTPs 6 to < 12 years of age) in Study CSL627_3002 does not reveal any safety concern.
- b) The rVIII-SingleChain PK in children is adequately characterized from Study CSL627_3002.

In addition, Arm 3 remained closed until the sponsor determined to open it. Arm 3 was opened in order to achieve a total of at least 200 PTPs for 100 EDs in Arms 1 and 3 combined. The sponsor contacted investigators directly when Arm 3 was open for enrollment.

rVIII-SingleChain will be administered intravenously (IV) at an actual dose and on a dosing schedule at the investigator’s discretion. This study will be conducted in compliance with this

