4.2 Subject Withdrawal

4.2.1 Subject Withdrawal

Subjects may withdraw from the study at any time at their own request, or they may be withdrawn at any time at the discretion of the investigator or CSL for safety, behavioral or administrative reasons (eg, due to an AE, protocol violation, subject noncompliance, and study termination).

In accordance with ICH principles of GCP, the investigator always has the option to advise a subject to withdraw from the study if the subject's safety or well-being is compromised by his or her further participation in the study. Concern for the interests of the subject must always prevail over the interests of the study.

If a subject is withdrawn from the study or further participation is declined, they will continue to have access to medical care and will be treated as per routine medical practice.

Arm 2 (PUPs):

In addition to the general withdrawal criteria described above, PUPs in Arm 2 **must be withdrawn** from the study if they develop any of the following withdrawal criteria:

- Use of any FVIII product other than rVIII-SingleChain (or its marketed available version) during the study (including if used as rescue medication).
- Subject develops a confirmed high-titer inhibitor (> 5 BU/mL confirmed by repeat testing at the central laboratory) but is not willing to participate in the **CCI** substudy.
- If the subject in the main study or the **CCI** substudy has successful inhibitor eradication and experiences inhibitor recurrence (relapse; ie, 2 consecutive inhibitor results \geq 0.6 BU/mL after eradication).

Further withdrawal criteria specific to the **CC1** substudy are defined in [Appendix 1](#).

Subjects with a **low-titer** inhibitor may either continue in the main study or can be enrolled into the **CC1** substudy (see [Appendix 1](#)), at the discretion of the investigator after discussion with the sponsor.

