4.2.3 Replacement Policy

Subjects withdrawn from the study will not be replaced.

5 Study Interventions

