## 4.11 Changes in Conduct or Planned Analyses from the Protocol

Section 2.1 and 2.2: In the protocol, incidence of inhibitor formation to FVIII in Arm 2, PUPs is stated that would be performed on at least 50 PUPs. However, this condition has been removed. Given that patients that develop inhibitors may be withdrawn from the study early, they would not necessarily achieve 50 exposure days but we would definitely have to include them in the calculation. Therefore the text was adjusted to ensure the option to properly report the endpoint regardless of these circumstances.

CCI

Section 3.5.3: Efficacy Population definition has been changed removing the exclusive inclusion of subjects who do not have an inhibitor at any time point during the study.

CCI

Section 4.6.1 and 4.6.2.1: In the Annualized Bleeding Rate analysis it has been added that subjects with an efficacy evaluation period less than 8 weeks (56 days) will be excluded from the analysis to exclude bias due to short evaluation period.

Section 4.6.2.2: The analysis of number of infusions of CSL627 required to achieve hemostasis has been added for completeness of analysis.

Section 4.7.1: Incidence of transient inhibitors has been added for completeness of analysis.

Section 4.7.2.1: Analysis of AESIs has been added for completeness of analysis.

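### Protocol 11.1 states the Arm 2 size as 24 PUPs completing 50 EDs and carries it unchanged into the enrolment total, while other sections give 24 with no ED condition or still say at least 50

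*Protocol*

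**What the plan says.** Protocol 11.1 states that no sample size calculation was performed. For the PTPs it says "The target enrollment is at least 200 PTPs (Arms 1 and 3) completing at least 100 EDs". For Arm 2, and for the total drawn from the two, it continues: "and 24 PUPs (Arm 2) completing 50 EDs of rVIII-SingleChain in this study. Thus, the study will enroll at total of least 224 subjects".

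Other sections describe the Arm 2 number differently:

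- **24, no exposure condition:** the protocol synopsis (Number of Subjects), Protocol 1.3, Protocol 3.5, and SAP 3.9 under Sample Size Estimation. Each gives it as a minimum.
- **At least 50 PUPs:** SAP 2.1 (primary endpoint), SAP 2.2.2 (inhibitor endpoints), SAP 3.1, and SAP 3.9 under Planned Number of Subjects.

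Three rules bear on whether enrolled PUPs become completers:

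- **Enrolment.** Protocol 1.3 reports an agreement "to stop enrolling subjects into Study CSL627_3001 and to continue treatment of the subjects currently enrolled".
- **Replacement.** Protocol 4.2.3: "Subjects withdrawn from the study will not be replaced".
- **Withdrawal.** Protocol 4.2.1 requires a PUP to be withdrawn for using another FVIII product, even as rescue. A further criterion is "Subject develops a confirmed high-titer inhibitor (> 5 BU/mL confirmed by repeat testing at the central laboratory) but is not willing to participate in the" substudy.

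Protocol 11.3.3.2 b) defines the denominator of the primary safety endpoint as PUPs with at least 50 EDs plus PUPs with fewer EDs who have a high-titer inhibitor.

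**The concern.** Twenty-four PUPs enrolled and 24 PUPs completing 50 EDs are different commitments. They coincide only if no PUP leaves early or if more than 24 were enrolled. Protocol 11.1 does not say which applies, and with recruitment stopped and no replacement, an early loss cannot be made good.

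What is at stake is the stated information content of Arm 2. A reader of 11.1 expects at least 24 evaluable PUPs for high-titer inhibitor incidence. A reader of the synopsis expects at least 24 boys in the arm, with an unstated number evaluable. A reader of SAP 2.1 expects at least 50. These imply different confidence intervals for the primary safety endpoint, and no section states the precision to be expected.

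**Working it through.** **1. Reproduce the plan's figure.** Inputs from Protocol 11.1: 200 PTPs and 24 PUPs, both worded as completers. 200 + 24 = 224, which matches the stated minimum enrolment. No alpha, power, effect size or precision target enters, so this sum is the only figure to check. It is right as addition and as a floor, and as a plan it implies attrition of zero.

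**2. What 24 completers would require.** Let d be the proportion of PUPs leaving before 50 EDs. The documents give no value, so a range is **assumed**. The PTP count is held at 200 because Protocol 1.3 describes that target as completed.

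- Enrolment needed for 24 completers: 24 / (1 − d), rounded up.
- If exactly 24 are enrolled: expected completers 24(1 − d); chance that all complete (1 − d)^24.
- If 28 are enrolled: chance of at least 24 completers = sum over k = 24 to 28 of C(28,k)(1 − d)^k d^(28−k).

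| Assumed d | PUPs needed (total) | Expected completers of 24 | Chance all 24 complete | Chance of ≥24 if 28 enrolled |
|---|---|---|---|---|
| 5% | 26 (226) | 22.8 | 29% | 99% |
| 10% | 27 (227) | 21.6 | 8% | 86% |
| 20% | 30 (230) | 19.2 | 0.5% | 31.5% |

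The result depends heavily on how many PUPs were enrolled, which the documents do not report.

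**3. Which losses count for the primary safety endpoint.** Suppose N are enrolled, h have a high-titer inhibitor and do not reach 50 EDs, and w others leave before 50 EDs.

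- Completers in the sense of 11.1: N − h − w.
- Denominator under 11.3.3.2 b): N − w.

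For illustration, N = 24, h = 3, w = 2 gives 24 − 3 − 2 = 19 completers and a denominator of 24 − 2 = 22. Only w reduces the primary denominator. The 11.1 target is therefore not the analysed set even when attrition is known.

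**4. Effect on precision.** With zero events the plan reports an upper one-sided 97.5% limit. The exact (Clopper-Pearson) value is 1 − 0.025^(1/n):

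| Evaluable n | Upper 97.5% limit at zero events |
|---|---|
| 24 | 14.2% |
| 22 | 15.4% |
| 20 | 16.8% |
| 18 | 18.5% |

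At a true rate of 20% (also an assumption), the expected width of the exact 95% interval goes from 33.6 points at n = 24 to 36.7 points at n = 20.

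**The case against.** The strongest reply is that nothing is shown to have gone wrong. Both 24 and 224 are minimums, 224 completers do need at least 224 enrolled, and stopping enrolment does not mean that exactly 24 PUPs were recruited. Protocol 3.5 promises a sufficient number of subjects, and that sentence governs the PUPs as well as the PTPs. No p-values or precision target are planned, the denominator is prespecified, and the interval will use the observed n. All of this stands. It limits the point to an inconsistent and incompletely stated sample size.

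A reader might infer more in three ways, none of which the documents support:

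- **That the stated size will not be delivered.** Actual Arm 2 enrolment and exposure status are not given. With 28 enrolled, 24 completers would be likely at 5% or 10% attrition.
- **That inhibitor withdrawals erode the primary denominator.** A PUP withdrawn after declining the substudy has a confirmed high-titer inhibitor, so 11.3.3.2 b) retains him. SAP 4.11 says of patients withdrawn early with inhibitors that "they would not necessarily achieve 50 exposure days but we would definitely have to include them in the calculation". Protocol 4.2.1 also lets low-titer PUPs continue in the main study.
- **That a dropout rate can be taken from the text.** The 35.4% in Protocol 1.1 is inhibitor incidence, not withdrawal. The Study CSL627_1001 counts in Protocol 1.4 are exposure reached by PTPs at the end of that study. Neither estimates attrition in PUPs.

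**Conclusion.** The point holds as a contradiction between sections and an omission in the stated size. Protocol 11.1 calls the 24 PUPs 50-ED completers, four other places give 24 without that condition, and four places in the SAP still say at least 50. The first two descriptions are compatible only with no loss before 50 EDs or with more than 24 enrolled, and the documents establish neither.

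A shortfall is possible, not demonstrated. If exactly 24 were enrolled, 5% to 20% attrition would leave about 19 to 23 completers. For the primary safety endpoint, the loss under 11.3.3.2 b) comes only from PUPs who leave before 50 EDs without a high-titer inhibitor, for example after using another FVIII product. Going from 24 to 20 evaluable PUPs would raise the zero-event upper limit by 2.6 points (16.8 − 14.2). These figures rest on the assumed attrition range and, for the completer counts, on enrolment of exactly 24. The effect on precision is modest and no analysis is invalidated, but the sample size statement should be corrected.

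**What to change.** 1. In Protocol 11.1, restate 24 as the minimum number of PUPs enrolled, or give the actual number enrolled, and remove the description of them as 50-ED completers.
2. Add that the evaluable number for the primary safety endpoint is the 11.3.3.2 b) set, and that it may be smaller than the number enrolled. It should not be declared to be below 24 unless the data show it.
3. State the exact precision over an assumed range of evaluable PUPs: zero-event upper 97.5% limits of 14.2%, 15.4%, 16.8% and 18.5% for n = 24, 22, 20 and 18.
4. Use the same Arm 2 figure throughout the SAP, replacing the remaining 50-PUP statements in 2.1, 2.2.2, 3.1 and 3.9 (Planned Number of Subjects). Correcting only the Sample Size Estimation paragraph would leave SAP 3.9 contradicting itself.

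The cost is a few sentences in Protocol 11.1 and matching edits in four SAP sections. It needs no further subjects, no new analysis and no change to any withdrawal or treatment rule. The stated precision may look slightly less favourable.

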11.2 Analysis Populations

All analyses in all analysis populations will be performed separately for PTPs and PUPs.

11.2.1 Enrolled Population

The Enrolled population will comprise all subjects who provided informed consent and were not screen failures.

11.2.2 Safety Population

The safety population will comprise all subjects in the Enrolled population who received at least 1 dose of rVIII-SingleChain during the study for any reason (eg, surgery, routine prophylaxis, on-demand treatment).

11.2.3 Efficacy Population

The efficacy population will consist of all subjects in the safety population who receive at least 1 dose of rVIII-SingleChain as part of either routine prophylaxis treatment or on-demand treatment during the study. Additionally, the efficacy population will only include subjects who do not have an inhibitor.

The Efficacy population might be the same as the Safety population.

11.2.4 Surgery Population

The Surgery population will include all subjects in the Safety population who received at least 1 dose of rVIII-SingleChain for surgical prophylaxis.

CCI

11.2.6 Pharmacokinetic Population

Not applicable.

11.2.7 Pharmacodynamic Population

Not applicable.

11.3 Statistical Analyses and Methods

All safety and efficacy data will be summarized or listed as appropriate. Continuous data will be summarized using descriptive statistics and categorical data will be summarized using frequency counts and percentages. There are no plans to produce p values. Confidence intervals (CIs) will be provided for key parameters where noted here or in the final statistical analysis plan. Except where otherwise noted, the CIs will be two-sided at the 95% level.

All analyses will be performed separately for PTPs and PUPs, including the analyses in the surgical substudy.

A complete description of the statistical analyses and methods will be available in the statistical analysis plan, which will be finalized before the database is locked.

11.3.1 Subject Disposition and Characteristics

11.3.1.1 Subject Disposition

The number of subjects who enrolled into this study, completed the study, withdrew from the study or discontinued the IMP will be presented in summary tables. The reason for discontinuing the IMP or withdrawing a subject from the study will be summarized.

The same methods will be applied to the substudies.

11.3.1.2 Subject Characteristics

Demographics and baseline subject characteristics will be presented in summary tables and data listings. Age will be described as both a continuous and a discrete variable. Supportive data will be listed by subject. A listing of gene abnormalities by subject will be prepared.

